### 5.2.2 Physiological Maturation

Physiological maturation is defined as an AVF having at least 500 mL / min of flow in the brachial artery and an outflow vein diameter of  $\geq 4 \text{ mm}$  as measured by DUS. Participants with AVFs that meet the definition of functional maturation (defined as successful prescribed HD with 2-needle cannulation of the AVF for three (3) continuous weeks) will automatically meet physiological maturation. This endpoint will be assessed through 6 weeks post creation. Additionally, for exploratory purposes, the endpoint will be assessed through 30 days, 3 months, 6 months, 12 months, 18 months, and 24 months post creation.

The event of physiological maturation will be identified if:

On the EndoAVF Dialysis page, Date of First 2-Needle Cannulation of 3 Week Continuous Dialysis is not NULL and within a specific visit (e.g., within 49 days for 6 weeks post creation). This meets the functional maturation.

or

On the Core Lab Analysis - Duplex Ultrasound: EndoAVF Arm page, Average Brachial Artery Volume Flow under the Brachial Artery/Vein Assessments section is >= 500 mL / min and any outflow vein diameter (including Distal Upper Arm Cephalic Vein Diameter, Mid Upper Arm Cephalic Vein Diameter, Proximal Upper Arm Cephalic Vein Diameter, Distal Upper Arm Basilic Vein Diameter, Mid Upper Arm Basilic Vein Diameter, Proximal Upper Arm Basilic Vein Diameter, Median Cubital Vein Diameter) under the Outflow Veins Section is >= 4 mm. In case the core lab DUS is not available, the corresponding information from the Duplex Ultrasound: EndoAVF Arm page will be used to determine the physiological maturation. Additionally, as a supportive analysis, only the core lab DUS data will be used to determine the physiological maturation. Data is considered not evaluable if the core lab DUS is not available.

The binary definition for physiological maturation is shown as below:

- If physiological maturation occurs on or before the end of a specific visit window (e.g., 42+7 = Day 49 for the 6-week visit), the participant is considered as having an event.
- If the participant was transferred to PD, or had a kidney transplant, or had access discontinuation, or discontinued before the beginning of a specific visit window (e.g., 42-7 = Day 35 for 6-week visit) without physiological maturation, the participant is considered not evaluable and will not be included in the analysis.
- Otherwise, if the participant did not achieve physiological maturation and has passed the specific visit
  window by the cutoff date of database lock, the participant is considered as not having an event. If the
  participant had access permanent abandonment prior to achieving physiological maturation and has passed
  the specific visit window by the cutoff date of database lock, the participant is considered as not having an
  event.

This endpoint will be evaluated on the AT population. The proportion of physiological maturation and the 95% two-sided CI will be provided using the Clopper-Pearson method. For the 6-month reporting, the physiological maturation rate up to 6-months (up to Day 210) will be presented. For the final reporting, the physiological maturation rate up to 24-months (up to Day 760) will be presented.

Similar analysis will be done for exploratory purposes, for physiological maturation defined as an AVF having at least 500 mL / min of flow in the brachial artery and an outflow vein diameter of  $\geq$  5 mm as measured by DUS.

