1.2 Schema

1.3 Schedule of Activities

		dure		Participant Follow-Up (Section 6.4)						4.2)	
	Screening (Section 6.1)	Screening / Index Procedure (Section 6.2)	Post-Index Procedure / Discharge (Section 6.3)	30-Day (± 5 days)	6-Week (± 7 days)	3-Month (± 30 days)	6-Month (± 30 days)	12-Month (± 30 days)	18-Month (± 30 days)	24-Month (± 30 days)	Unscheduled (Section 6.4.2)
In-Clinic Visit	✓	✓	✓	√ †	✓		✓	✓			✓
Phone Call				†		✓			✓	✓	✓
Informed Consent	✓										
Eligibility	✓	✓									
Demographics / Medical History	✓										
Angiography (Procedural & Final)		✓									
DUS	✓	✓		✓	✓		✓ *	*			#
Clinical Exam	✓		✓	>	>		>	>			✓
Medication Assessment		✓									
QOL - EQ-5D Questionnaire	✓				✓		✓	✓		✓	#
QOL - SF-VAQ	✓				✓		✓	✓		✓	#
HD History and Status**	✓	✓		✓	✓	✓	✓	✓	✓	✓	✓
Intervention Assessment			✓	√ †	✓	✓	✓	✓	>	✓	✓
Adverse Event Assessment		✓	✓	√ †	✓	✓	✓	✓	✓	✓	✓
Deviations		✓	✓	√ †	✓	✓	✓	✓	✓	✓	✓

^{*} DUS required at these visits only if participant is not successfully dialyzing with the AVF created as part of this clinical investigation using 2-needle cannulation and / or if the participant's wrist artery was used for procedure access during the index procedure.

For participants into whom the WavelinQTM EndoAVF system was introduced but procedure success was not achieved, only the follow up at 30 days is required to collect adverse events and interventions. The visit for these participants may be completed by phone. Investigation participation for these participants ends after completion of this follow-up.

^{**}Determine and document if and how the participant has been and / or is receiving HD (AVF, CVC, etc.) and document the date of the participant's last HD session. Once HD (1- or 2-needle cannulation) is initiated via the AVF created as part of this investigation, HD details must be documented and detailed HD access data (e.g., cannulation logs) will be provided to the Sponsor or designee for review and analysis as per Section 6.4.1.

^{*} These items are required for those unscheduled visits that fall within an allotted investigation schedule follow-up window if the visit is used in place of an investigation scheduled follow-up for which these items are required.

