6.4 Participant Follow-Up

6.4.1 Follow-Up Intervals and Methods

All participants are to be followed according to the investigational site's SOC practices. In addition to the SOC visits, treated participants will have an investigation follow-up visit at 30-days and 6-weeks as well as 6- and 12-months post index procedure and will have a phone call follow-up at 3-, 18- and 24-months. For participants into whom the WavelinQTM EndoAVF System was introduced during the index procedure but procedure success was not achieved, only the follow up at 30-days will be completed and limited to the collection of safety events and interventions. This follow-up may be conducted by phone for these participants and investigation participation for these participants will end upon completion of this follow-up.

All follow-up must be performed by authorized delegated clinical investigation site team members. Follow-up windows will be calculated from the index procedure date. Refer to Section 1.3 for an overview of follow-up window time frames and requirements for each visit. The following data will be collected and documented on the appropriate eCRF for each follow-up unless otherwise specified for treated participants:

- DUS: A DUS assessment per the Ultrasound Guidelines must be performed at the follow-up visits at 30-days and 6-weeks for all treated participants and again at 6-and 12-months for participants not yet successfully dialyzing with the AVF created as part of this clinical investigation using 2-needle cannulation. The 6- and 12-month DUS are also required for participants that are using the AVF created as part of this clinical investigation but for whom procedure access was obtained at the wrist artery during the index procedure. The DUS for these participants will be limited to the examinations of the artery that was accessed during the index procedure. At minimum, images including the following characteristics are required and must be submitted to the Sponsor / Core Lab as per the details specified in the investigational site's regulatory binder:
 - o Arteries and veins of the AVF: Patency (including characterization of each stenosis, if present), and inner diameters. Brachial artery volume flow.
 - AV-anastomosis & juxta-anastomotic area: Patency (including characterization of each stenosis, if present).
 - o Cannulation veins: Patency (including characterization of each stenosis, if present) and inner diameters.

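### Exploratory physiological maturation is reported through 3, 18 and 24 months with no duplex ultrasound (DUS) scheduled behind those times, and the 6- and 12-month DUS waiver does not match the automatic credit

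*SAP*

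**What the plan says.** SAP 5.2.2 defines physiological maturation by DUS: brachial artery flow of at least 500 mL/min and an outflow vein of at least 4 mm. Functional maturation is an alternative route: "successful prescribed HD with 2-needle cannulation of the AVF for three (3) continuous weeks) will automatically meet physiological maturation". The secondary endpoint is at 6 weeks. For exploratory purposes the SAP adds that "the endpoint will be assessed through 30 days, 3 months, 6 months, 12 months, 18 months, and 24 months post creation", and the final report presents the rate up to Day 760.

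A participant has an event if maturation occurs by the end of the visit window. A participant without an event is not evaluable after transfer to peritoneal dialysis (PD), transplant, access discontinuation or exit before the window opens. A missing DUS is not on that list. The default rule begins "Otherwise, if the participant did not achieve physiological maturation and has passed the specific visit" and classifies such participants as no event. Permanent abandonment before maturation is also a no-event.

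Under Protocol 6.4.1, DUS "must be performed at the follow-up visits at 30-days and 6-weeks for all treated participants". At 6 and 12 months it is conditional; the Schedule of Activities (Protocol 1.3) states "DUS required at these visits only if participant is not successfully dialyzing with the AVF created as part of this clinical investigation" by two-needle cannulation, or if the wrist artery was used for procedure access. For wrist-access participants who are using the fistula, Protocol 6.4.1 adds: "The DUS for these participants will be limited to the examinations of the artery that was accessed during the index procedure". Treated participants otherwise "will have a phone call follow-up at 3-, 18- and 24-months".

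**The concern.** A rate reported through a given time is normally read as what was known about the fistulas by then. Here three of the seven reporting times (30 days, 6 weeks, and 3, 6, 12, 18 and 24 months) have no scheduled measurement of flow or diameter since a much earlier visit. The curve from 6 weeks to 3 months, and from 12 to 24 months, would then largely reflect the visit schedule and dialysis uptake, not fistula development. A fistula that first reaches the thresholds between scans counts as no event, in the same way as one that was scanned and fell short.

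At 6 and 12 months the issue is narrower. The condition that removes the scan and the condition that grants credit without a scan differ, so a participant can fall between them and be scored a non-event while dialyzing through the fistula.

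**Working it through.** **Inputs.** Visit windows from Protocol 1.3 and SAP 5.2.2 and 5.2.4; DUS requirements from Protocol 1.3 and 6.4.1; scoring rules from SAP 5.2.2; 150 treated participants with assumed attrition of 20%, 40% and 60% at 6, 12 and 24 months from SAP 2.4.

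**1. Windows.** The SAP's own figures reproduce: 42 − 7 = Day 35, 42 + 7 = Day 49, 180 + 30 = Day 210, 730 + 30 = Day 760. By the same rule the 6-month window opens at 180 − 30 = Day 150, and the 12-month window is 365 ± 30 = Days 335–395.

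**2. Intervals without scheduled DUS that contain a reporting time.**
- Between the 6-week and 6-month windows: Days 50–149, or 149 − 50 + 1 = 100 days. Taking 3 months as Day 90 (an assumption; the SAP gives no day), its window of Days 60–120 lies wholly inside.
- After the 12-month window: Days 396–760, or 760 − 396 + 1 = 365 days. This holds the 18- and 24-month contacts.

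Protocol 1.3 requires DUS at an unscheduled visit only when that visit replaces a scheduled one that needs it. The SAP event rule does not limit itself to scheduled scans, so an incidental DUS could still count.

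**3. Tracing the rules.**
- Not on HD, no qualifying scan by 6 weeks: no event at 3 months, because functional maturation is out of reach. A full DUS follows at 6 and 12 months. Status at 18 and 24 months then repeats the 12-month result until HD starts.
- A qualifying scan at any earlier visit: stays an event at every later time.
- Two-needle dialysis at the 6- or 12-month visit, no earlier qualifying scan, and no three-week run starting by the end of the window: scan waived, no credit, scored no event. With wrist access a scan is done, but only of the accessed artery, so flow and vein diameter are still missing.

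**4. Size of one misclassification.** Retained numbers are 150 × 0.8 = 120, 150 × 0.6 = 90 and 150 × 0.4 = 60. One mature fistula scored no event costs 100/120 = 0.83, 100/90 = 1.11 or 100/60 = 1.67 points at 6, 12 or 24 months. These ignore PD, transplant and access discontinuation. They are otherwise upper limits, since participants who matured before leaving stay in the denominator.

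**5. Illustration at 6 months** (assumed: 120 evaluable, 75% truly mature, so 90).

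| Mature but unscanned | Planned rule | If removed from denominator |
|---|---|---|
| 2 | 88/120 = 73.3% | 88/118 = 74.6% |
| 6 | 84/120 = 70.0% | 84/114 = 73.7% |
| 12 | 78/120 = 65.0% | 78/108 = 72.2% |

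If instead the 6 unscanned participants were all immature, the planned rule would give the correct 90/120 = 75.0%, and removal would give 90/114 = 78.9%. Removal can therefore err upward.

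**6. Denominator.** Events are kept after a participant leaves, while non-mature leavers drop out. Assume 75% mature at 6 weeks, no later maturation, and attrition unrelated to maturity. The reported rate becomes 0.75/(0.75 + 0.25 × 0.8) = 78.9% at 6 months, 0.75/(0.75 + 0.25 × 0.6) = 83.3% at 12 and 0.75/(0.75 + 0.25 × 0.4) = 88.2% at 24. A late rate can rise with no new maturation at all.

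**The case against.** The strongest reply is that the endpoint is cumulative. Under the schedule, everyone scored no event at 3 months has had two scans, and a participant who stays off two-needle dialysis with the fistula has four by 12 months. A rate through a phone contact is then a defined quantity: earlier DUS results plus functional maturation. That stands, and it is why relabelling is an acceptable alternative to deletion. The SAP does not now describe the rates that way. Its other DUS-based patency endpoint (SAP 5.3.11) is confined to 6 weeks.

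Several stronger readings are tempting but not supported:
- That the secondary endpoint is compromised. At 6 weeks DUS is required for all treated participants, so neither the schedule nor the waiver reaches it. Only a missed 6-week scan would fall under the default rule.
- That the waiver harms incident participants. While not on HD they keep full DUS at 6 and 12 months; for them the issue is confined to the three phone contacts, and maturation missed at 3 months can be picked up at 6.
- That intermittent dialyzers as a group are lost. Credit is dated to the first day of the three-week run, so a run that starts inside the window and ends after it still counts. The documents also give no duration for successful dialysis, so reading intermittent use as meeting the waiver is an inference.
- That the core-lab supportive analysis, which makes a missing core-lab DUS not evaluable, contradicts the main rule. A supportive analysis may handle missing data differently.
- That the 3-month rate is understated by a known amount. A figure of 10 points follows if 20% first mature in the gap and half of them are not yet functionally mature, but both inputs would be invented.

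**Conclusion.** The point holds for exploratory results only, and its priority is low. Three of seven reporting times rest on no scheduled DUS, with gaps of 100 and 365 days. The status of participants not yet on HD at those times repeats an earlier scan. At 6 and 12 months the mismatch between waiver and credit leaves a narrow group with neither scan nor credit.

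Scoring unscanned mature fistulas as no event works against the device, by at most about 0.83 points each at 6 months and 1.11 at 12 under the SAP's attrition assumptions. The documents do not allow the number of such participants to be estimated. The retained denominator pulls late rates the other way, so the net direction at 24 months cannot be stated. The conclusion rests on the written schedule being followed and on few unscheduled scans.

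**What to change.** In SAP 5.2.2:
1. Report DUS-based physiological maturation only at 30 days, 6 weeks, 6 months and 12 months.
2. Drop the 3-, 18- and 24-month (Day 760) rates, or present them explicitly as the last scheduled DUS carried forward plus functional maturation, with the number evaluable beside each.
3. Keep the present rules that an earlier qualifying DUS counts, functional maturation counts, and permanent abandonment before maturation is a non-event.
4. At 6 and 12 months, state how many participants scored no event had no in-window DUS of flow and vein diameter. Add a best-case/worst-case analysis for them (all mature, then none). Do not make them not evaluable: that could raise the rate, as step 5 shows, and a blanket rule would also override the scoring of abandonment.

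The cost is a few exploratory table columns and one small sensitivity table, with no new data collection. Separately, the Protocol passages on the waiver (1.3 and 6.4.1, including "12-months for participants not yet successfully dialyzing with the AVF created as part of this clinical investigation using 2-needle cannulation") and on the three-week credit (4.2.2 and 4.3) should be reconciled. Protocol 6.4.1 also attaches a 75%-of-sessions threshold to the three-week period that 4.3 does not. The SAP changes do not depend on that reconciliation.

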4.4 Applicable Endpoint Definitions

Access Abandonment (permanent abandonment) is defined as the point at which the access can no longer be used for one or two needle prescribed HD as it may be unable to provide adequate flows and / or is deemed unsafe for the participant, and the associated problem cannot be corrected by any further intervention, including medical, surgical, or endovascular interventions or rest.^{8,19} Participants with an abandoned index AVF will continue with follow-up through 24-months and data will be collected on safety and interventions.

A HD AV access is not considered abandoned:

- If the participant discontinues use of the AV access due to kidney transplant, initiation of PD, or participant preference.
- During the maturation period or while waiting for a second stage procedure unless the principal investigator (PI) determines the participant requires and they then receive an alternative HD vascular access.

- During planned interventions, including transposition.
- If all reasonable efforts have not been attempted (and documented) to improve the condition of the access for it to be used.

A discontinuation of use of the clinical investigation AVF for any reason that does not meet this definition of access abandonment will be considered a temporary interruption.

Access Circuit Censoring Events include participant transfer to PD, kidney transplantation or the event of a participants premature discontinuation in the investigation due to withdrawn consent, withdrawal by PI, Lost to Follow-Up (LTF), or participant death (refer to Section 6.5 for definitions).

Adjunctive Procedure(s): Procedure(s) completed during the index procedure (prior to leaving the procedure room) as part of Standard-of-Care (SOC) procedures. These may include procedures to facilitate maturation and / or cannulation of the AVF, procedures to maintain use of the AVF, procedures to ensure HD continuity, as well as procedures to address AFs.

Second Stage Procedure(s): Facilitation Interventions (as defined below) intended to support the cannulation of arterialized vein segments that are determined to be needed a priori to or at the time of the index procedure (i.e. pre-planned facilitation interventions intended to support cannulation). Second stage procedures will not count against the intervention or patency endpoints and will require completion of the Second Stage Procedures eCRF.

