## 2.7 Endpoints

Note: The term access abandonment is synonymous with permanent abandonment for the purposes of these investigation documents. Access abandonment (permanent abandonment) is an abandonment that meets the definition in Section 4.4 of the CIP. The term access discontinuation is used to refer to any discontinuation of use of the access that does not meet these criteria of the definition and may also be referred to as a "temporary interruption" as per the CIP.

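### As ordered, the physiological maturation rule can drop known failures (fistulas permanently abandoned before maturing) from the later exploratory rates, biasing those rates upward

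*SAP*

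**What the plan says.** The rule is in SAP 5.2.2. Six weeks is the secondary time point; for exploratory purposes "the endpoint will be assessed through 30 days, 3 months, 6 months, 12 months, 18 months, and 24 months post creation". The estimator is a crude proportion among evaluable participants in the AT population, with a Clopper-Pearson interval.

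The binary definition has three bullets, in this order:

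1. Success: "If physiological maturation occurs on or before the end of a specific visit window", the participant has the event. Later exit does not undo this.
2. Exclusion: after PD transfer, transplant, access discontinuation or study discontinuation before the window opens, "without physiological maturation, the participant is considered not evaluable and will not be included in the analysis".
3. Failure: "Otherwise, if the participant did not achieve physiological maturation and has passed the specific visit" window by the database-lock cutoff, the participant is a non-event. A second sentence in this bullet scores as a non-event the case where the "participant had access permanent abandonment prior to achieving physiological maturation and has passed" the window.

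Three definitions bear on this:

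- Protocol 4.4 reserves permanent abandonment for an access where "the associated problem cannot be corrected by any further intervention".
- Protocol 4.4 keeps such participants in the study: "Participants with an abandoned index AVF will continue with follow-up through 24-months and data will be collected on safety and interventions".
- SAP 2.7 separates the two kinds of stopping: "The term access discontinuation is used to refer to any discontinuation of use of the access that does not meet these criteria" for permanent abandonment. Abandonment alone therefore does not trigger the second bullet; a later study exit, PD transfer or transplant does.

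**The concern.** Take a fistula permanently abandoned on Day 90 without having matured, in a participant who dies on Day 250. At 6 months (window opening on Day 150) the participant is a failure. At 12 months (window opening on Day 335) the participant left before the window without maturing, so the second bullet applies and the participant is removed. The same happens at 18 and 24 months. Nothing about maturation was unknown when the participant died.

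A participant who matured and died on the same day stays in every later rate as a success. The exclusion can remove only non-events, so its direction is fixed. Part of any rise in the maturation rate between 6 and 24 months could then come from attrition among known failures. The additional analysis at a 5 mm vein diameter inherits the same rule.

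**Working it through.** **Is there a plan figure to reproduce?** No. Neither document states an expected maturation rate, a rate of abandonment before maturation, or a power for this endpoint.

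**Comparison within the SAP.** In SAP 5.2.4 (cumulative functional patency), permanent abandonment is scored in the first bullet, and the not-evaluable bullet is limited to those who left without it. In SAP 5.1.1 (primary safety), the SAE is likewise scored before evaluability is considered. In 5.2.2 the not-evaluable bullet excepts prior maturation but not prior abandonment.

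**Inputs from the documents.** N = 150 treated; attrition 20%, 40% and 60% at 6, 12 and 24 months (SAP 2.4); window half-widths of 7 days at 6 weeks and 30 days from 3 months on (Protocol 1.3).

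**Assumptions not in the documents.** A fraction of 5, 10 or 20% is abandoned before maturing, on Day 30, 60 or 90. A further 10% never mature for other reasons. The rest mature and are all counted. Abandoned participants leave at the general attrition rate.

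**Formulas.** Let M = matured, A = abandoned before maturing, U = otherwise not matured. S(t) is the share still in the study on day t, piecewise exponential through 0.80, 0.60 and 0.40 on Days 180, 365 and 730. For a window opening on day w and abandonment on day a, the share of A lost is d = 1 − S(w)/S(a), or 0 if w ≤ a.

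- Bullets in SAP order: M / [M + A(1 − d) + U·S(w)]
- Abandonment scored first: M / [M + A + U·S(w)]

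**Central case.** 10% abandoned on Day 60, so A = 15, U = 15, M = 120 and S(60) = 0.928.

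| Time point | w | S(w) | d | Known failures lost | SAP order | Abandonment first | Difference (points) |
|---|---|---|---|---|---|---|---|
| 6 weeks | 35 | 0.958 | 0 | 0 | 80.3% | 80.3% | 0 |
| 6 months | 150 | 0.830 | 0.106 | 1.6 | 82.3% | 81.4% | 0.9 |
| 12 months | 335 | 0.629 | 0.323 | 4.8 | 86.0% | 83.1% | 2.9 |
| 18 months | 517 | 0.507 | 0.454 | 6.8 | 88.4% | 84.2% | 4.2 |
| 24 months | 700 | 0.414 | 0.555 | 8.3 | 90.3% | 85.0% | 5.3 |

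For example, at 24 months: 120/(120 + 15 × 0.445 + 15 × 0.414) = 120/132.9 = 90.3%, against 120/(120 + 15 + 15 × 0.414) = 120/141.2 = 85.0%.

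**Range over 5 to 20% abandoned and Days 30 to 90.** 6 weeks: 0 to 0.1 points. 6 months: 0.3 to 2.1. 12 months: 1.4 to 5.7. 24 months: 2.7 to 10.3.

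**Second model.** A simulation spread abandonment evenly over Days 30 to 180, maturation evenly over Days 25 to 60, and used linear attrition between the same points. With 5% abandoned (80% maturing and a quarter of the rest abandoned) it gives about 0.2, 1.2 and 2.4 points at 6, 12 and 24 months. Together the two models give the rounded ranges of 0.2 to 2, 1 to 6 and 2.5 to 10 points.

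**What reordering leaves behind.** In the central case true maturation is 120/150 = 80.0%. At 24 months the SAP order gives 90.3% and the reordered rule 85.0%. Reordering removes 5.3 of the 10.3 points; the other 5.0 come from dropping unmatured leavers whose fistula was not abandoned.

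**The case against.** **The text can be read the other way.** The abandonment sentence was written for this case, and having passed the window by the database-lock cutoff can mean that calendar time has elapsed. Elsewhere (SAP 5.1.1, 5.3.5, 5.3.8) the SAP says explicitly when a participant must be in the investigation; 5.2.2 does not. On that reading the Day 90 abandonment is a failure at every time point. This stands as far as it goes. A reader might infer that abandonment counts as failure only if the participant stays in the study, but the SAP does not say so. The calendar reading, however, does not switch off the second bullet, which still fits the same participant and comes first. The two rules then classify one participant differently.

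**The operative derivation is not visible.** SAP 3.2 points to Appendix 2, whose content is not in the documents and may resolve the order. The body text should still agree with it.

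**Little depends on it.** The 6-week secondary rate is practically untouched, no hypothesis is tested, and Protocol 7.6 says exploratory endpoints may not be reported. No ultrasound is scheduled after 12 months (Protocol 1.3), so the 18- and 24-month rates largely carry earlier status forward. All true, although SAP 5.2.2 does commit to presenting the rate up to 24 months in the final report.

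**The upper sizes are generous.** Pre-market 6-month cumulative patency of 77.3% (Protocol 2.1.2) leaves a 22.7% loss. It is tempting to assign nearly all of that to abandonment before maturation and expect 5 to 10 points at 24 months. The documents do not support this: the loss is not confined to immature fistulas, Protocol 2.1.1 reports an abandonment after a cannulation injury, and Protocol 4.4 restricts abandonment during maturation.

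**Abandonments are reported elsewhere.** Cumulative patency (SAP 5.3.8) counts them when they occur, and SAP 6.16 summarises them. They are not hidden, but that does not correct the maturation rate.

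**Conclusion.** The concern holds as a minor point about rule order. Read in sequence, SAP 5.2.2 excludes known maturation failures who later leave, transfer to PD or are transplanted before a window opens, and keeps matured participants who leave. Read with calendar time, it contradicts itself for the same participants. Where the exclusion operates, its direction is certain and favours the device.

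The size is much less certain. It rests on the plan's attrition figures and on an assumed 5 to 20% abandoned before maturing, with assumed timing. The effect is practically nil at 6 weeks, small at the 6-month reporting, and material only in the 12- to 24-month exploratory rates if abandonment before maturation is common. It does not touch either co-primary endpoint or the secondary time point.

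**What to change.** In SAP 5.2.2, place a rule ahead of the evaluability bullet: permanent abandonment before physiological maturation is a non-event at that and every later time point, whatever PD transfer, transplant or discontinuation follows. Limit the not-evaluable bullet to participants with neither prior maturation nor prior permanent abandonment, on the model of SAP 5.2.4. Check that the derivation in Appendix 2 and the 5 mm analysis follow the same order.

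The cost is one sentence and, if Appendix 2 follows the present order, a reordered derivation. No new data are needed, and the exploratory rates become slightly less favourable. The SAP should also say that unmatured leavers without abandonment remain excluded, so the later rates are still conditional on evaluability and should be read that way.
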